**Attachment 3: Conversion Table for Glucocorticosteroid Dose**

| Glucocorticoid      | Approximate Equivalent Dose (mg) | Half-life (Biologic) hours |
|---------------------|----------------------------------|----------------------------|
| Intermediate-Acting |                                  |                            |
| Methylprednisolone  | 4                                | 18-36                      |
| Prednisolone        | 5                                | 18-36                      |
| Prednisone          | 5                                | 18-36                      |
| Triamcinolone       | 4                                | 18-36                      |
| Long-Acting         |                                  |                            |
| Betamethasone       | 0.6 – 0.75                       | 36-54                      |
| Dexamethasone       | 0.75                             | 36-54                      |

#### Attachment 4: As of Protocol Amendment 5, Study Drug Administration and Required Study Evaluations for Subjects Remaining in Treatment Extension or Follow-up

**Note:** All assessments are to be performed locally. As of Amendment 5, central laboratory evaluations are not applicable.

|   | Notes   | Treatment Extension Phase   | EOT | Follow-up |
|---|---|---|-----|-----------|
| Study Drug Administration. Refer to Site investigational Product Procedures Manual and appropriate Investigational Product Preparation Instructions for recommendations on daratumumab administration details (including IV infusion rate, SC dose duration). |   |   |     |           |
| Subjects in Treatment Extension Phase   | Includes daratumumab IV and daratumumab SC dosing   | X (Day 1 of each cycle)   |     |           |
| Pre-dose Medications   |   |   |     |           |
| Methylprednisolone  | Methylprednisolone 100 mg for first 2 doses, 60 mg for all subsequent doses (in the absence of infusion-related AEs in the first 2 doses). Substitutions allowed, see Attachment 3. | approximately 1 hr prior to every dose of daratumumab   |     |           |
| H1-antihistamine  | Diphenhydramine 25-50 mg, cetirizine 10 mg, or equivalent   | approximately 1 hr prior to every dose of daratumumab   |     |           |
| Paracetamol   | Paracetamol or acetaminophen 650-1000 mg  | approximately 1 hr prior to every dose of daratumumab   |     |           |
| Montelukast   | Montelukast 10 mg (optional)  | approximately 1 hr prior to every dose of daratumumab   |     |           |
| Post-Dose Medications  |   |   |     |           |
| Methylprednisolone  | Methylprednisolone 20 mg/day orally. Substitutions allowed, see Attachment 3.   | Required after all doses for subjects in Treatment Extension Phase who experienced an IRR during Cycle 1 (exception made for steroid intolerance); may be offered in conjunction with the first dose and subsequent doses of daratumumab SC for subjects who switch dosing routes; per investigator discretion for all other subjects/cycles. |     |           |

**Attachment 4: Dosing Administration and Required Study Evaluations as of Protocol Amendment 5 for Subjects Remaining in Treatment Extension or Follow Up (Continued).**

|   | Notes  | Treatment Extension Phase  | EOT | Follow-up  |
|---|--|--|-----|--|
| Other Study Procedures   |  |  |     |  |
| Hematology  | To be performed by local lab and reported in the CRF   | Prior to every dose of daratumumab: hemoglobin, white blood cell count with absolute neutrophils and lymphocytes, platelet count.          | X   | After completion of study treatment, obtain with disease assessments until PD.                     |
| Clinical Chemistry  |  | Day 1 of each cycle of daratumumab administration: uric acid, total bilirubin, creatinine, blood urea nitrogen, AST, ALT, ALP, LDH         | X   | Creatinine only:
After completion of study treatment, obtain with disease assessments until PD. |
| Weight  | If a subject's weight changes by more than 10% from baseline, the dose of study drug will be re-calculated for subjects receiving daratumumab IV | Day 1 of each cycle of daratumumab IV administration   |     |  |
| Vital Signs   | Vital signs (blood pressure, temperature) measured in sitting position for subjects receiving daratumumab IV                                     | Day 1 of each cycle of daratumumab IV administration immediately before administration start and at end of each daratumumab administration |     |  |
| The start of each cycle may occur $\pm 5$ days of the scheduled day in order to accommodate the schedule of the site or subject. After EOT, subjects in all treatment arms prior to PD will continue to return for local disease evaluations per Standard of Care. After PD is documented, subjects will be followed only for survival; subsequent anticancer therapy, and occurrence of other malignancies every 6 months. |  |  |     |  |

**Attachment 4: Dosing Administration and Required Study Evaluations as of Protocol Amendment 5 for Subjects Remaining in Treatment Extension or Follow Up (Continued).**

|                        | Notes   | Treatment Extension Phase  | EOT | Follow-up |
|------------------------|---|--|-----|-----------|
| Procedures             |   |  |     |           |
| ECOG                   | Once a subject discontinues or completes therapy prior to PD, ECOG will only be assessed at the End-of-Treatment Visit and additionally when PD is suspected.   | Q16W during the Treatment Extension Phase  | X   |           |
| 12-lead ECG            |   |  | X   |           |
| Physical exam          | clinically significant abnormalities should be reported as AEs  | symptom and disease directed exam as clinically indicated  |     |           |
| Laboratory Assessments |   |  |     |           |
| Pregnancy test         |   | as clinically indicated  |     |           |
| HBV DNA test           | For subjects with serologic evidence of resolved HBV infection (ie, positive Anti-HBs or positive Anti-HBc) at Screening, HBV DNA testing by PCR must be performed locally. Refer to Section 9.5.2.   | Q12W during treatment, at the End of Treatment / EOT Extension Visit, and Q12W for up to 6 months after the last dose of study treatment |     |           |
| Disease Evaluations    | To be performed locally per Standard of Care. Progressive disease as determined by the Investigator must be reported to the Sponsor. Local SPEP/UPEP/FLC data are not to be recorded in the CRF. Evaluation of response is to be recorded in the CRF. | until progressive disease is determined  |     |           |

**Attachment 4: Dosing Administration and Required Study Evaluations as of Protocol Amendment 5 for Subjects Remaining in Treatment Extension or Follow Up (Continued).**

|                                      | Notes                                     | Treatment Extension Phase   | EOT | Follow-up |
|--------------------------------------|---|---|-----|-----------|
| Bone marrow aspirate                 |   | For subjects with suspected PD, bone marrow aspirate should be assessed locally per standard of care for percentage of plasma cells and reported in the CRF. After PD, no additional collections are required.  |     |           |
| Skeletal radiography, or low-dose CT |   | Use same methodology during study as used at screening and report results in the CRF:
Skeletal radiography or low-dose CT q12 months, and at biochemical progression (eg, increase in SPEP >25%) or at suspected PD.
For subjects with (1) negative MRI results at baseline, (2) M-protein increase $\leq$ 25%, and (3) no other signs of clinical progression, only an MRI needs to be performed. For these subjects, low-dose whole body CT or skeletal survey does not need to be repeated unless focal lesions have been identified by MRI. After PD, no additional assessments are required. |     |           |
| MRI of spine and pelvis              |   | q6 months for the first 3 years, then q12 months, and at biochemical progression (eg, increase in SPEP >25%) or at suspected PD; whole body MRI per local practice or when clinically indicated. Results should be entered in the CRF. After PD, no additional assessments are required.  |     |           |
| Second primary malignancy            |   |   |     | X         |
| Subsequent Anti- myeloma Therapy     | Record both treatment and response.       |   |     | X         |
| Survival                             |   |   |     | X         |
| Ongoing Subject Review        |   |   |     |           |
| Adverse Events                       | See Section 12 for detailed instructions. | continuous from the time of signing of ICF until 30 days after last dose of last study treatment  |     |           |
| Concomitant Medications              | See Section 8 for detailed instructions.  | continuous from the time of signing of ICF until 30 days after last dose of last study treatment  |     |           |

Abbreviations: AE=adverse event; ALP= alkaline phosphatase; ALT= alanine aminotransferase; anti-HB= anti- hepatitis B antigen; anti-HBc= hepatitis B core antigen; AST= aspartate aminotransferase; CRF=case report form; CT= computed tomography; ECOG=Eastern Cooperative Oncology Group; ECG=electrocardiogram; EOT=End-of-Treatment; FLC=free light chain; HBV= hepatitis B virus; ICF=informed consent form; IRR= infusion-related reaction; IV=intravenous; LDH=lactate dehydrogenase; MRI=magnetic resonance imaging; PCR=polymerase chain reaction; PD= disease progression; SC=subcutaneous; SPEP=serum M-protein quantitation by electrophoresis; UPEP=urine M-protein quantitation by electrophoresis; W=week

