### **Amendment 6** (29 March 2021)

**The overall reason for the amendment:** The overall reason for the amendment is to extend the study duration up to a maximum of 7 years following Last Patient First Dose (LPFD) by redefining the End of Study.

| Applicable Section(s)  | Description of Change(s)   |
|--|--|
| Rationale: The end of the study was extended to collect long-term safety and efficacy data and to allow subjects to have the option to continue to receive study treatment. |  |
| Synopsis, Overview of Study Design (including figure); 3.1. Overview of Study Design; Figure 1; 3.2. Study Design Rationale; 9.1.4. Follow-up Phase; 17.9.1. Study Completion      | The end of study definition was changed to occur up to approximately 7 years after the last subject's first dose, not approximately 5 years.

Text regarding the evaluation of data from a Phase 3 study to potentially extend drug treatment beyond the end of study was deleted.   |
| Rationale: Text was added to specify permitted and prohibited vaccinations.   |  |
| 8.1. Permitted Therapies   | Text was added indicating vaccinations are allowed per local guidelines with a reference to Section 8.2.   |
| 8.2. Prohibited Therapies  | Text was added clarifying the restriction of live attenuated and replication-competent viral vector vaccines.  |
| Rationale: Clarified procedures in Attachment 4.  |  |
| Attachment 4   | Clarified that on Day 1 of each cycle, only subjects receiving daratumumab IV may require a recalculation of weight and should have vital signs measured.

Added text to the table to indicate that the administration of pre-dose methylprednisolone should be administered in the absence of infusion-related adverse events in the first 2 doses. |
| Rationale: Minor errors were noted  |  |
| Throughout the protocol  | Minor grammatical, formatting, or spelling changes were made.  |

**Amendment 5** (01 April 2020)

**The overall reason for the amendment:** Overall reasons for the amendment are 1) to extend the study duration and 2) to provide flexibility for study investigators as it relates to the global coronavirus (COVID-19) pandemic.

The overall reason for the amendment is to extend the study duration to approximately 5 years following Last Patient First Dose (LPFD) by redefining the End of Study. This amendment also reduces required assessments in the Time and Events Schedule for ongoing subjects.

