## 3.2. Study Design Rationale

### Rationale for Study Design

Randomization in the assignment of subjects to a dosing schedule will allow assessment of preliminary efficacy and safety across all 3 arms. To further minimize imbalance across treatment arms and to allow for important subgroup analyses, subjects will be stratified according to the number of risk factors present at screening ( $<2$  versus  $\geq 2$ ) using the criteria of Dispenzieri (2013). These risk factors will include: abnormal free light chain (FLC) ratio ( $<0.126$  or  $>8$ ), serum M-protein  $\geq 3$  g/dL, urine M-protein  $>500$  mg/24 hours, IgA subtype, and immunoparesis (at least 1 uninvolved immunoglobulin [IgG, IgA, IgM] decreased more than 25% below lower limit of normal [LLN]). Stratification factors will be based on central laboratory analyses.

The treatment effect, evaluating whether initial response will reduce the rate of progression to symptomatic MM or death in subjects with intermediate or high-risk SMM, will be measured using the endpoint of PFS, defined as the time between randomization and progression to symptomatic MM or death. Given that the median time to progression in the high-risk SMM patient population is about 2 years, assessment of PFS rate approximately 1 year after the last subject is randomized should provide an early indication of treatment effect. However, all subjects will continue to be followed, and in the final study analysis (expected up to approximately 7 years after the last subject's first dose), long-term data on PFS will be analyzed.

[figure not shown]
The criteria for efficacy (both response and follow up to progression to symptomatic MM, as defined by the IMWG, are objective and will be measured in all 3 treatment dosing schedules. The CR rate is defined as the proportion of subjects with CR. In a recent Phase 3 study of lenalidomide and dexamethasone in high-risk SMM patients, CR rate in the maintenance phase was 26% [Mateos 2013]. A correlation between CR and time to symptomatic MM has been demonstrated in simulation models conducted by the Janssen statistical team. A CR rate of 35% was chosen as the alternative hypothesis for this study, since a CR rate of at least 30% is considered to be most likely to translate into delay of progression to myeloma.

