#### 9.2. Efficacy

As of Amendment 5, refer to Attachment 4 for a description of study procedures for subjects who continue in the Treatment Extension Phase or who have discontinued treatment but remain in Follow-up. Disease assessments will be performed at Week 5, Week 9, and then every 8 weeks in the first year, thereafter every 16 weeks (including treatment extension/re-initiation phase) until disease progression. A window of  $\pm 7$  days before the scheduled assessment date is allowed. For subjects with treatment delays, disease assessments should be performed at the time of daratumumab administration, but do not need to be repeated if they were performed within 14 days before the actual treatment date. Disease progression, if based on laboratory results only, must be confirmed by a consecutive assessment.

Disease assessments will be performed by a central laboratory (unless otherwise specified) according to Table 1. Disease progression to symptomatic MM will be evaluated using the IMWG criteria (Rajkumar 2014). For subjects who discontinue study drug before disease progression, disease assessments should continue to be performed as scheduled until disease progression, death,

withdrawal of consent for study participation, or the end of the study. Disease assessments scheduled for treatment days should be collected before study drug is administered.

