### 9.2.1.2. Assessment of Disease Progression to Multiple Myeloma

For data analysis and reporting, the sponsor will use a computer algorithm to objectively and consistently implement the IMWG diagnostic criteria for MM requiring systemic therapy. During the study, disease progression will be measured according to the published international uniform diagnostic criteria for MM requiring systemic therapy established by the IMWG (Rajkumar 2014) presented in Table 5.

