5.3.3.2. Analysis Methods

Analysis of PFS will be based on the ITT analysis set. The Kaplan-Meier method will be used to estimate the distribution of PFS for each treatment group. Median PFS with 90% CI will be provided. In addition, the number and percentage of subjects who had a PFS event or were censored will be reported. The Kaplan-Meier PFS curve by treatment group will also be provided.

A similar analysis of PFS based on investigator assessment will also be conducted.

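### After Amendment 5 the progression algorithm has no FLC or calcium data, and no rule says how long-term PFS joins the periods before and after

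*Protocol*

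**What the plan says.** **Aim.** Protocol Section 3.2 (Rationale for Study Design) states that "in the final study analysis (expected up to approximately 7 years after the last subject's first dose), long-term data on PFS will be analyzed". The Amendment 5 rationale names PFS, with safety and overall survival, as a reason for longer follow-up.

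**How progression is derived.** Protocol Section 9.2.1.2: "For data analysis and reporting, the sponsor will use a computer algorithm to objectively and consistently implement the IMWG diagnostic criteria". The criteria are the seven in Table 5. Sections 9.2 and 9.2.1.2 require progression that rests on laboratory results alone to be confirmed by a repeat. SAP 5.3.3.1 defines PFS by SLIM-CRAB progression or death, and SAP 5.3.3.2 adds: "A similar analysis of PFS based on investigator assessment will also be conducted".

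**What changes with Amendment 5.** Attachment 4 makes all assessments local, ends central laboratory evaluations, and has the investigator determine progression and report it to the sponsor. It adds: "Local SPEP/UPEP/FLC data are not to be recorded in the CRF". Its chemistry list includes creatinine but neither calcium nor albumin. After end of treatment, "subjects in all treatment arms prior to PD will continue to return for local disease evaluations per Standard of Care".

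**What the SAP says about the join.** Nothing. SAP Section 1.2 still describes a study ending about 4 years after the last subject's first dose.

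**The concern.** The plan extends follow-up partly to obtain long-term PFS, but stops collecting two of the inputs that its own derivation of progression uses. Three analyses are then possible at the final cutoff:

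- Run the algorithm to the end. A subject whose only progression is by FLC ratio or calcium counts as progression-free until another criterion is met or the subject dies.
- Splice algorithm calls before Amendment 5 to investigator calls after it. One curve then mixes two ways of ascertaining the event.
- Use investigator-assessed PFS throughout.

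The documents do not choose. The study is open-label, so the choice would be made with the data in view.

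FLC is an awkward value to lose. Section 9.2.1.3 says that daratumumab can artificially raise the ratio and has produced ambiguous progression calls. After Amendment 5, an investigator's FLC-based call can reach the sponsor without the number behind it.

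**Working it through.** The plan gives no figure to reproduce on this point. The check is a comparison of passages, followed by an illustration of size.

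**1. Table 5 criteria against Attachment 4**

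| Criterion | Data after Amendment 5 | Evaluable by the algorithm? |
|---|---|---|
| Calcium | Not in the schedule; central testing ended | No |
| Renal insufficiency | Creatinine on Day 1 of each cycle, then with disease assessments | Yes |
| Anemia | Hemoglobin before every dose, then with disease assessments | Yes |
| Bone lesions | Imaging every 12 months and at suspected progression, in the CRF | Yes |
| Marrow plasma cells ≥60% | Percentage at suspected progression, in the CRF | Yes |
| FLC ratio ≥100 | Expressly not recorded | No |
| More than 1 focal lesion on MRI | Fixed calendar and at suspected progression, in the CRF | Yes |

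Two of seven cannot be evaluated. The repeat test cannot be checked for FLC-only or calcium-only progression. It can be for anemia and renal progression, because serial hemoglobin and creatinine continue. SPEP and UPEP are not Table 5 criteria, so of the three tests named in the no-recording sentence only FLC affects PFS.

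**2. Share of events in the later period**

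Inputs: rate 0.185 per patient-year (Section 11.2, alternative hypothesis); 40 subjects per arm; study end at 7 years. The primary PD/death cutoff is 12 months after last randomization, and the Amendment 5 rationale says that about 3 further years of data had been collected after the primary analysis. That puts Amendment 5 at about 1 + 3 = 4 years after last randomization; I use 3.5 to 4.5.

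With S(t) = exp(−0.185t), the share of events by year 7 that occur after time a is [S(a) − S(7)] / [1 − S(7)], where S(7) = 0.274.

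- a = 4: (0.477 − 0.274) / 0.726 = 28%. Per arm, 40 × 0.726 = 29 events, of which 40 × 0.203 = 8 are late.
- a = 3.5: (0.523 − 0.274) / 0.726 = 34%.
- a = 4.5: (0.435 − 0.274) / 0.726 = 22%.
- Subject randomized one year before the last (Amendment 5 at year 5, study end at year 8): (0.396 − 0.228) / (1 − 0.228) = 22%.

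**3. Hemoglobin and creatinine checks**

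On extension (Arms A and B only) these are taken every 8 weeks. Off treatment, which includes all of Arm C, they are taken with standard-of-care assessments that have no stated interval. With exponential PFS at L = ln 2 / 3.75 = 0.185 per year and checks every t years, mean detection delay is t / (1 − exp(−Lt)) − 1/L. The off-treatment interval is an assumption, varied from 12 to 52 weeks.

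| Interval | Mean delay | Mean observed PFS relative to 8-week checks |
|---|---|---|
| 8 weeks | 4.0 weeks | reference |
| 12 weeks | 6.0 weeks | +0.7% |
| 16 weeks | 8.1 weeks | +1.4% |
| 26 weeks | 13.2 weeks | +3.2% |
| 52 weeks | 26.8 weeks | +8.0% |

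These are upper bounds for each interval. They treat every event as found through these two tests and apply the gap to all follow-up and to every Arm A and B subject.

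**The case against.** **The algorithm may not apply after Amendment 5.** Section 9.2.1 says that its subsections describe evaluations required before Amendment 5, and 9.2.1.2 is one of them. This stands as a reading, but it moves the gap rather than closing it: if the algorithm has lapsed, no derivation rule for analysis replaces it.

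**Investigator-assessed PFS is already in the SAP.** It is, and it can run from randomization to study end. That makes the fix cheap. The SAP lists it as an additional analysis and does not say which version is the long-term result.

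**Stronger readings that a reader might infer, and that the documents do not support:**

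- *The algorithm has lost its inputs altogether.* Five of seven criteria still have data.
- *Disease evaluations run on 8-week cycles during extension.* The Disease Evaluations row of Attachment 4 puts them on standard of care and does not limit this to subjects off treatment. Only dosing and safety laboratory tests follow the cycle. Imaging follows one calendar in all arms.
- *Attachment 4 contradicts Section 9.2.* Section 9.2 says "thereafter every 16 weeks (including treatment extension/re-initiation phase) until disease progression", but it opens by sending the reader to Attachment 4 as of Amendment 5.
- *Amendment 5 created the unequal checks.* Hemoglobin and creatinine already followed dosing on treatment (Table 3) and disease assessments off treatment (Table 1). Amendment 5 removed the fixed off-treatment interval.
- *Amendment 6 lengthened the study specifically for PFS.* Its stated reason is broader: "The end of the study was extended to collect long-term safety and efficacy data", together with continued treatment. PFS is named in the Amendment 5 rationale and in Section 3.2.
- *PFS will certainly be overstated.* Against Table 5 as written, an algorithm without FLC and calcium can only call progression later or not at all. Given the FLC artefact described in 9.2.1.3, some of the lost calls may not be true progression.

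**Conclusion.** The point holds in limited form. For data after Amendment 5, two of the seven progression criteria cannot be evaluated by the stated algorithm, and FLC-only or calcium-only progression cannot be confirmed. Ascertainment moves from central data plus algorithm to local investigator determination, with no rule joining the two periods. The written definition of PFS does not change; the way events are found does.

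Roughly a fifth to a third of PFS events by year 7 would fall in the later period. This assumes a constant 0.185 per year, no dropout, follow-up to the full 7 years (the protocol says up to approximately 7), and the Amendment 5 timing above. Accrual time is not given, and earlier-randomized subjects would have a smaller share. The documents do not allow an estimate of how many late events would be FLC-only or calcium-only, so the bias itself cannot be sized.

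The unequal hemoglobin and creatinine checks are a limitation to state, not a separate defect. The SAP plans Kaplan-Meier summaries of PFS by arm and no between-arm test. The co-primary analyses are unaffected, since the Amendment 5 rationale says that the primary analysis had already been reported.

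**What to change.** 1. In SAP 5.3.3, state that the final long-term PFS is investigator-assessed, from randomization to study end, in all arms.
2. In the same section, keep algorithm PFS as a supportive analysis, censored at each subject's last central-laboratory disease assessment before Amendment 5.
3. In Attachment 4, require for progression events only that the CRF record the criterion met, its value and date, and the confirmatory value, including FLC and calcium.
4. Note as a limitation that hemoglobin and creatinine are checked every 8 weeks on extension (Arms A and B only) but at standard-of-care intervals off treatment, and that local work-up may change after Amendment 5 even under a single investigator-assessed endpoint.

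The cost is a few lines in the SAP, one short form per progression event, and the loss of late follow-up from the algorithm-based PFS. No added visits are needed, and a fixed minimum assessment interval is not part of this recommendation: Amendment 5 reduced required assessments deliberately.
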